7. INTERIM ANALYSIS

No formal interim analysis is planned for this study.

An analysis for one data snapshot is planned. The Safety analysis set (SAF) will be used for safety analyses. Week 24 completer set will be used for efficacy analyses.

Week-24 Completer Set (For Data Snapshots Prior to Database Lock)

The week 24 completer population includes all participants who have completed the week 24 study, and the patients who could have completed their week 24 assessments had they not prematurely withdrawn from the study (i.e. These patients are early dropouts, and their baseline dates are (168 + 7) days earlier than each data-cut date)

8. SOFTWARE

All analyses will be done using SAS Version 9.4 or above.

10. APPENDIX

10.1. Summary of Statistical Analyses

Efficacy Analysis:

Endpoint	Analysis Population	Primary Statistical Method	Supportive Statistical Method	Subgroup Analysis	Other Analyses
Continuous variables	FAS	Descriptive Statistics	No	Yes	No
Categorical variables	FAS	Descriptive Statistics	No	Yes	No

Safety Analyses:

Endpoint	Analysis Populations	Statistical Method	Supportive Analysis	Subgroup Analysis	Other Analyses
Adverse Events	SAF	Descriptive Statistics	No	No	No

10.2. Schedule of Events

Study assessments and procedures for original global are presented by study period and visit in [Table 1](#).

Table 1: Schedule of Events

Table 1: Schedule of Events¹		TREATMENT PERIOD									
Study Procedure	SCNV1 ²	BL V2	Ph V3	V4	V5	V6	V7	V8	V9	ET Visit ³	EOT / EOS V10
Week (W)			W1	W2	W4	W8	W12	W16	W20		W24
Day (D)	D-35 to D-1	D1	D8	D15	D29	D57	D85	D113	D141		D169
Visit Window (Days [d])			±3 d	±3 d	±3 d	±7 d	±7 d	±7 d	±7 d		±7 d
Screening/Baseline:											
Inclusion/Exclusion ⁴	X	X									
Fitzpatrick skin type	X										
Informed consent/assent ⁵	X										
Informed consent/assent for optional pharmacogenomics substudy ⁵	X										
Informed consent/assent for optional future biomedical research substudy ⁵	X										
Informed consent/assent for optional use of photographs (selected study sites only) ⁵	X										
Informed consent/assent for optional colorimetry substudy (selected study sites only) ⁵	X										
Informed consent/assent for optional OCT and non-invasive in vivo imaging substudy (single study site only) ⁵	X										
Skin-type characterization questionnaire ⁶		X									
Medical history	X										

Table 1: Schedule of Events ¹		TREATMENT PERIOD									
Study Procedure	SCNV1 ²	BL V2	Ph V3	V4	V5	V6	V7	V8	V9	ET Visit ³	EOT / EOS V10
Week (W)			W1	W2	W4	W8	W12	W16	W20		W24
Day (D)	D-35 to D-1	D1	D8	D15	D29	D57	D85	D113	D141		D169
Visit Window (Days [d])			±3 d	±3 d	±3 d	±7 d	±7 d	±7 d	±7 d		±7 d
POEM ⁶		X		X	X	X	X	X	X	X	X
Patient Global Impression of Disease ⁶		X		X	X	X	X	X	X	X	X
Patient Global Impression of Change ⁶				X	X	X	X	X	X	X	X
Investigator Reported:											
EASI	X	X		X	X	X	X	X	X	X	X
IGA	X	X		X	X	X	X	X	X	X	X
SCORAD		X		X	X	X	X	X	X	X	X
BSA	X	X		X	X	X	X	X	X	X	X
AD phenotypic description ¹³		X		X	X	X	X	X	X	X	X
Post-inflammatory hyperpigmentation severity scale (PHSS)		X		X	X	X	X	X	X	X	X
Photography (select sites) ¹⁴		X						X		X	X
Colorimetry measurement (select sites) ¹⁵		X		X	X	X	X	X	X	X	X
Optical Coherence Tomography and non-invasive in vivo imaging (single site) ¹⁶		X			X			X		X	X

Table 1: Schedule of Events ¹		TREATMENT PERIOD									
Study Procedure	SCNV1 ²	BL V2	Ph V3	V4	V5	V6	V7	V8	V9	ET Visit ³	EOT / EOS V10
Week (W)			W1	W2	W4	W8	W12	W16	W20		W24
Day (D)	D-35 to D-1	D1	D8	D15	D29	D57	D85	D113	D141		D169
Visit Window (Days [d])			±3 d	±3 d	±3 d	±7 d	±7 d	±7 d	±7 d		±7 d
POEM ⁶		X		X	X	X	X	X	X	X	X
Patient Global Impression of Disease ⁶		X		X	X	X	X	X	X	X	X
Patient Global Impression of Change ⁶				X	X	X	X	X	X	X	X
Investigator Reported:											
EASI	X	X		X	X	X	X	X	X	X	X
IGA	X	X		X	X	X	X	X	X	X	X
SCORAD		X		X	X	X	X	X	X	X	X
BSA	X	X		X	X	X	X	X	X	X	X
AD phenotypic description ¹³		X		X	X	X	X	X	X	X	X
Post-inflammatory hyperpigmentation severity scale (PHSS)		X		X	X	X	X	X	X	X	X
Photography (select sites) ¹⁴		X						X		X	X
Colorimetry measurement (select sites) ¹⁵		X		X	X	X	X	X	X	X	X
Optical Coherence Tomography and non-invasive in vivo imaging (single site) ¹⁶		X			X			X		X	X

Table 1: Schedule of Events ¹		TREATMENT PERIOD									
Study Procedure	SCNV1 ²	BL V2	Ph V3	V4	V5	V6	V7	V8	V9	ET Visit ³	EOT / EOS V10
Week (W)			W1	W2	W4	W8	W12	W16	W20		W24
Day (D)	D-35 to D-1	D1	D8	D15	D29	D57	D85	D113	D141		D169
Visit Window (Days [d])			±3 d	±3 d	±3 d	±7 d	±7 d	±7 d	±7 d		±7 d
Medication history	X										
Demographics	X										
Patient diary training ⁷	X										
Treatment:											
Injection training of study drug		X									
Administer dupilumab ^{8,9,10}		X		X	X	X	X	X	X		
Patient diary recording dosing information		X	X	X	X	X	X	X	X		
Concomitant Medications/procedures	X	X	X	X	X	X	X	X	X	X	X
Efficacy¹⁰											
Patient Reported:											
Peak Pruritus NRS ^{6,11}										X (daily)	
Sleep Quality NRS ^{6,11}										X (daily 7 days prior to each visit)	
Skin Pain NRS ⁶		X		X	X	X	X	X	X	X	X
Dyspigmentation NRS ⁶		X		X	X	X	X	X	X	X	X
Xerosis NRS ⁶		X		X	X	X	X	X	X	X	X
CDLQI ^{6,12} , DLQI ^{6,12}		X		X	X	X	X	X	X	X	X
HADS ⁶		X		X	X	X	X	X	X	X	X

Table 1: Schedule of Events ¹		TREATMENT PERIOD									
Study Procedure	SCNV1 ²	BL V2	Ph V3	V4	V5	V6	V7	V8	V9	ET Visit ³	EOT / EOS V10
Week (W)			W1	W2	W4	W8	W12	W16	W20		W24
Day (D)	D-35 to D-1	D1	D8	D15	D29	D57	D85	D113	D141		D169
Visit Window (Days [d])			±3 d	±3 d	±3 d	±7 d	±7 d	±7 d	±7 d		±7 d
POEM ⁶		X		X	X	X	X	X	X	X	X
Patient Global Impression of Disease ⁶		X		X	X	X	X	X	X	X	X
Patient Global Impression of Change ⁶				X	X	X	X	X	X	X	X
Investigator Reported:											
EASI	X	X		X	X	X	X	X	X	X	X
IGA	X	X		X	X	X	X	X	X	X	X
SCORAD		X		X	X	X	X	X	X	X	X
BSA	X	X		X	X	X	X	X	X	X	X
AD phenotypic description ¹³		X		X	X	X	X	X	X	X	X
Post-inflammatory hyperpigmentation severity scale (PHSS)		X		X	X	X	X	X	X	X	X
Photography (select sites) ¹⁴		X						X		X	X
Colorimetry measurement (select sites) ¹⁵		X		X	X	X	X	X	X	X	X
Optical Coherence Tomography and non-invasive in vivo imaging (single site) ¹⁶		X			X			X		X	X

Table 1: Schedule of Events ¹		TREATMENT PERIOD									
Study Procedure	SCNV1 ²	BL V2	Ph V3	V4	V5	V6	V7	V8	V9	ET Visit ³	EOT / EOS V10
Week (W)			W1	W2	W4	W8	W12	W16	W20		W24
Day (D)	D-35 to D-1	D1	D8	D15	D29	D57	D85	D113	D141		D169
Visit Window (Days [d])			±3 d	±3 d	±3 d	±7 d	±7 d	±7 d	±7 d		±7 d
Safety: ¹⁰											
Physical Examination	X									X	X
Weight / Height	X									X	X
Adverse Events ¹⁷	X	X	X	X	X	X	X	X	X	X	X
Laboratory Testing: ^{10, 19a}											
Pregnancy Test (Urine, WOCBP only)		X		X	X	X	X	X	X	X	X
Pharmacokinetics Sampling: ¹⁸											
Drug conc. sample ¹⁹		X					X			X	X
Biomarkers: ¹⁹											
Total serum IgE and allergen-specific IgEs		X			X		X			X	X
Exploratory Research Serum/Plasma		X			X		X			X	X
Future Biomarker Serum/Plasma (optional)		X			X		X			X	X
Pharmacogenomics:											
Whole blood for DNA (optional) ²⁰		X									

Abbreviations: BL = baseline; BSA = body surface area; CDLQI = Children's Dermatology Life Quality Index; DLQI = Dermatology Life Quality Index; EASI = Eczema Area and Severity Index; HADS = Hospital Anxiety and Depression Scale; IGA = Investigator's Global Assessment; IgE = Immunoglobulin E; NRS = numerical rating scale; Ph = Phone; SCN = screening; SCORAD = SCORing Atopic Dermatitis; WOCBP = women of childbearing potential

10.3. Detailed Description of Efficacy Endpoints

Eczema Area and Severity Index (EASI)

The EASI is a validated measure used in clinical practice and clinical trials to assess the severity and extent of AD ([Hanifin 2001](#)). The EASI score calculation is based upon the Physician's Assessment of Individual Signs [erythema (E), induration/papulation (I), excoriation (X), and lichenification (L)], where each sign is scored as 0 = Absent, 1 = Mild, 2 = Moderate, or 3 = Severe, and also upon the Area Score [based on the % (BSA) affected] where 0 = 0% BSA, 1 = 1-9% BSA, 2 = 10-29% BSA, 3 = 30-49% BSA, 4 = 50-69% BSA, 5 = 70-89% BSA, 6 = 90-100% BSA.

For each of major section of the body (head, upper extremities, trunk and lower extremities), EASI score = $(E+I+X+L) \times \text{Area Score}$. The total EASI score is the weighted total of the section EASI using the weights 10% = head, 20% = upper extremities, 30% = trunk, 40% = lower extremities. The minimum possible EASI score is 0 and the maximum possible EASI score is 72 where a higher score indicates increased extent and severity of atopic dermatitis. The EASI score of each sign (E, I, X and L) can be calculated in a similar way, for example, the EASI score of erythema = weighted sum of E x Area Score at each section.

EASI will be collected at the scheduled and unscheduled clinic visits as indicated in Section [10.2](#).

Investigator's Global Assessment (IGA)

The IGA is a static 5-point assessment instrument to rate AD disease severity globally in clinical studies. The ratings (0 = clear, 1 = almost clear, 2 = mild, 3 = moderate, 4 = severe) are an overall assessment of AD skin lesions based on erythema and papulation/infiltration. IGA score will be assessed at every scheduled and unscheduled clinic visits as indicated in Section [10.2](#).

SCORing Atopic Dermatitis (SCORAD)

The SCORAD is a validated tool used in clinical research and clinical practice that was developed to standardize the evaluation of the extent and severity of AD ([Dermatology 1993](#)). The extent of AD is assessed by the Investigator as a percentage of each defined body area and reported as the sum of all areas, with a maximum score of 100% (assigned as "A" in the overall SCORAD calculation). The severity of 6 specific symptoms (erythema, oedema / papulation, excoriations, lichenification, oozing / crusts and dryness) of AD is assessed by the Investigator using the following scale: none (0), mild (1), moderate (2), or severe (3) (for a maximum of 18 total points, assigned as "B" in the overall SCORAD calculation). Subjective assessment of itch and sleeplessness is recorded for each symptom by the patient or relative on a visual analogue scale (VAS), where 0 is no itch (or sleeplessness) and 10 is the worst imaginable itch (or sleeplessness), with a maximum possible score of 20. This parameter is assigned as "C" in the overall SCORAD calculation. The SCORAD is calculated as $A/5 + 7B/2 + C$. The maximum SCORAD score is 103. The SCORAD will be assessed at time points as indicated in Section [10.2](#).

Peak Pruritus NRS (PP NRS)

The PP NRS is a simple assessment tool that participants will use to report the intensity of their pruritus (itch) during a 24-hour recall period. Participants will be asked the following question:

For maximum itch intensity: “On a scale of 0 to 10, with 0 being ‘no itch’ and 10 being the ‘worst itch imaginable’, how would you rate your itch at the worst moment during the previous 24 hours?”

Participants will be instructed on using the participant diary to record their PP NRS at the screening visit. Participants will complete the rating scale daily throughout the entire study (baseline and preceding 7 days and treatment period; see Section 10.2.). Clinical sites will check and remind the participant to complete the diary according to the time points in Section 10.2..

For each day, if there are multiple NRS scores collected on the same day, the maximum value of all the scores collected will be used for analysis.

The baseline NRS is defined as the prorated average of the NRSs reported continuously for 7 days right before and on the baseline visit (i.e. study day -6 to day 1). For post-baseline NRS, the mean weekly NRS is calculated as the prorated average of the reported daily NRS within the week. For example, if there are 3 scores in a week, the prorated average = (score1 + score2 + score3)/3.

Body Surface Area Affected by Atopic Dermatitis

The BSA affected by AD will be assessed for each major section of the body (the possible highest score for each region is: head and neck [9%], anterior trunk [18%], back [18%], upper limbs [18%], lower limbs [36%], and genitals [1%]) and will be reported as a percentage of all major body sections combined. Patients will undergo this assessment at baseline and subsequent study visits as indicated in Section 10.2.

Dermatology Life Quality Index (DLQI)

The DLQI is a 10-item, validated questionnaire ([Badia 1999](#)) used in clinical practice and clinical trials to assess the impact of AD disease symptoms and treatment on Quality of Life (QoL). The format is a simple response to 10 items, which assess QoL over the past week. For each item, the scale is rated as follows: 0=’not at all’=’not relevant’; 1=’a little’; 2=’a lot’; 3=’very much’=’yes’ in question 7, with an overall scoring system of 0 to 30; a high score is indicative of a poor QoL. The DLQI will be assessed at time points according to in Section 10.2.

- Handling missing items from DLQI
 - i. If one question is left unanswered this is scored 0 and the scores are summed and expressed as usual out of a maximum of 30.
 - ii. If two or more questions are left unanswered the questionnaire is not scored.
 - iii. If question 7 is answered 'yes' this is scored 3 even if in the same question one of the other boxes is ticked.
 - iv. If question 7 is answered 'no' or 'not relevant' but then either 'a lot' or 'a little' is ticked this is then scored 2 or 1.
 - v. If two or more response options are ticked for one question, the response option with the highest score should be recorded.

vi. The DLQI can be analyzed by calculating the score for each of its six sub-scales. When using sub-scales, if the answer to one question in a sub-scale is missing, that sub-scale should not be scored:

Symptoms and feelings	Questions 1 and 2	Score maximum 6
Daily activities	Questions 3 and 4	Score maximum 6
Leisure	Questions 5 and 6	Score maximum 6
Work and School	Question 7	Score maximum 3
Personal relationships	Questions 8 and 9	Score maximum 6
Treatment	Question 10	Score maximum 3

Children's Dermatology Life Quality Index (CDLQI)

The CDLQI is a validated questionnaire designed to measure the impact of skin disease on the QOL in children ≥ 4 years of age ([Lewis-Jones 1995](#)). The aim of the questionnaire is to measure how much a patient's skin problem has affected the patient over a recall period of the past week. In this study, a cartoon version of the CDLQI will be administered to patients 4 to 5 years of age, with the assistance of a parent or adult "as necessary". If assistance of parent or adult caregiver is required, it is recommended that the same person assist the patient throughout the study. The cartoon version of the CDLQI uses the same text and scoring system as the original CDLQI but includes 10 color drawings of a dog illustrating the theme of each question.

To complete the questionnaire, patients need to provide responses to 10 questions (the questions focus on domains such as symptoms feelings associated with disease, the impact of the disease on leisure, school or holidays, personal relationships, sleep, and side effects of treatment for the skin disease. The instrument has a recall period of 7 days. Nine of the 10 questions are scored as follows:

- Very much = 3
- Quite a lot = 2
- Only a little = 1
- Not at all = 0
- Question unanswered = 0

Question 7 has an additional possible response (prevented school), which is assigned a score of 3. Overall scoring ranges from 0 to 30; a high score is indicative of a poor QOL. The CDLQI will be assessed at the scheduled and unscheduled clinic visits according to Section [10.2](#).

Handling missing items from CDLQI:

- i. If one question is left unanswered this is scored 0 and the scores are summed and expressed as usual out of a maximum of 30.
- ii. If two or more questions are left unanswered the questionnaire is not scored.

- iii. If two or more response options are ticked for one question, the response option with the highest score should be recorded.
- iv. The CDLQI sub-scores may be analyzed by calculating the score for each of its six sub-scales. When using sub-scales, if the answer to one question in a sub-scale is missing, that sub-scale will not be scored:

Sub-scales	Questions	Maximum Score
Symptoms and feelings	Questions 1,2	6
Leisure	Questions 4, 5 and 6	9
School or holidays	Question 7	3
Personal relationships	Questions 3 and 8	6
Sleep	Question 9	3
Treatment	Question 10	3

Patient Oriented Eczema Measure (POEM)

The POEM is a 7-item, validated questionnaire used in clinical practice and clinical trials to assess disease symptoms in children and adults with atopic eczema ([Charman 2004](#)). The format is patient response to 7 items (dryness, itching, flaking, cracking, sleep loss, bleeding, and weeping) based on symptom frequency during the past week (i.e., 0 = 'no days', 1 = '1 to 2 days', 2 = '3 to 4 days', 3 = '5 to 6' days, and 4 = 'every day'). The total score is the sum of the 7 items which is ranged from 0 to 28; a high score is indicative of a poor QOL. The following POEM banding scores have been established (Charman 2004): 0 to 2 = Clear or almost clear; 3 to 7 = Mild eczema; 8 to 16 = Moderate eczema; 17 to 24 = Severe eczema; 25 to 28 = Very severe eczema. If two or more response options are selected for a question, then the response option with the highest score is recorded. If one question of the seven is left unanswered, then that question is scored as 0 and the scores are summed and expressed as usual out of a maximum of 28. If two or more questions are left unanswered, then the questionnaire is not scored and is set to missing. If two or more response options are ticked for one question, the response option with the highest score should be recorded. Higher score indicates worse condition.

Hospital Anxiety and Depression Scale (HADS)

The HADS is a Likert-scale tool widely used to detect states of anxiety and depression in a general hospital setting ([Bjelland 2002](#)). The 14 items on the questionnaire, assessing how the patient has been feeling in the past week, include 7 items that are related to anxiety (odd numbered questions) and 7 items that are related to depression (even numbered questions). Questions 2, 4, 7, 9, 12, and 14 are scored from 0 (less distress) to 3 (greater distress) according to the content of the item. Questions 1, 3, 5, 6, 8, 10, 11, and 13 are reverse scored from 0 (greater distress) to 3 (less distress).

A person can score between 0 and 21 for each subscale (anxiety and depression). A high score is indicative of a poor state. Scores of 11 or more on either subscale are considered to be a 'definite case' of psychological morbidity, while scores of 8–10 represents 'probable case' and 0–7 'not a case' ([Zigmond 1983](#)).

For each sub-scale: if one question is missing, the response will be imputed as the mean of the remaining six questions. If more than one question is missing, then the subscale is set to missing. The total score is the sum of the two sub-scores.

HADS will be assessed at time points according to Section [10.2](#).

Skin Pain NRS

Skin pain will be measured using a skin pain NRS that was developed and tested for the study-relevant age group. This is an 11-point scale (0 to 10) in which 0 indicates no pain while 10 indicates worst pain possible. SP NRS can be categorized as: no pain (0), mild (1 to 3), moderate (5 to 6), severe (7 to 9), and very severe (10). The threshold for minimally clinically important difference for SP NRS is between 2.2 to 2.9 ([Silverberg, 2021](#)). The SP NRS will be performed at time points according to Section [10.2](#).

Adult patients will be asked the following question:

- “On a scale of 0 to 10, with 0 being ‘no skin pain or soreness’ and 10 being ‘the worst possible skin pain or soreness’, how would you rate your skin pain or soreness overall, which is on average, during the past 7 days?”

Adolescent patients (≥ 12 to < 18 years at baseline) will be asked the following question:

- “Think about all the areas of your skin with eczema. How would you rate your skin pain at its worst in the past 7 days?”

Patients will be asked to complete this assessment at baseline and then approximately every month throughout the study as indicated in Section [10.2](#).

The baseline Skin Pain NRS score is defined as the prorated average of the Skin Pain scores reported continuously for 7 days right before the baseline visit (i.e. study day -7 to day -1). For post-baseline Skin Pain NRS score, the weekly mean of daily Skin Pain score is calculated as the average of the available reported skin pain score within the week. For example, if there are 3 scores available in a week, the prorated average = $(\text{score1} + \text{score2} + \text{score3})/3$.

Sleep Quality NRS

Study patients will be asked to rate their sleep quality on their past night upon awakening, using the Sleep Quality NRS, ranging from 0 (“Worst possible sleep”) to 10 (“Best possible sleep”). Sleep Quality NRS are to be collected daily including 7 days immediately preceding the baseline visit and then daily during the week before each planned visit.

Patients will be instructed on using the patient diary to record their Sleep Quality NRS at the screening visit. Clinical sites will check and remind the patient to complete the diary according to the time points in Section [10.2](#).

The baseline Sleep Quality NRS score is defined as the prorated average of the sleep quality NRS scores reported continuously for 7 days right before the baseline visit (i.e. study day -7 to day -1). For post-baseline Sleep quality NRS score, the weekly mean of daily sleep quality score is calculated as the average of the available reported daily sleep quality score within the week. For example, if there are 3 scores available in a week, the prorated average = (score1 + score2 + score3)/3.

Patient Global Impression of Disease (PGID)

The PGID is an assessment instrument used by the patient in clinical studies to rate their eczema symptoms during the past 7 days.

Patients will rate their disease based on the 5-level scale as follows:

“Overall, how would you rate your eczema symptoms during the past 7 days?”

- No symptoms
- Mild
- Moderate
- Severe
- Very severe

The PGID score will be assessed at time points according to Section [10.2](#)

Patient Global Impression of Change (PGIC)

PGIC will be measured using a patient administered tool.

Patients will respond to the following question based on the 7-level scale as follows:

“Compared to before you started the study, how would you rate your eczema now?”

- Much better
- Moderately better
- A little better
- No change
- A little worse
- Moderately worse
- Much worse

The PGIC is an instrument used by the patient in clinical studies to compare their eczema symptoms from the beginning of the study to when they completed the assessment.

The PGIC score will be assessed at time points according to Section [10.2](#).

Colorimetry Measurement (Sub-study)

Colorimetry for melanin index and erythema index at AD lesional, hyperpigmentation lesional, and non-lesional targets (select sites) – At select study sites, melanin and erythema indices will be measured by handheld colorimeter probe applied to a representative area of AD (EASI erythema and papulation severity subscore each >0), a representative area of hyperpigmentation (PHSS >1 and EASI erythema and papulation severity subscore each = 0), and a representative area of background non-lesional skin (PHSS ≤ 1 and EASI erythema and papulation severity subscore each = 0). Efforts should be made to select photoprotected targets (to minimize confounding from UV exposure) and targets within the same anatomical region (trunk, upper extremity, lower extremity) or on the contralateral side. Subsequent measurements of the same sites will be taken at time points according to Section 10.2.

Signature Page for VV-TMF-3607081 v1.0

Reason for signing: Approved	Name: [REDACTED]
	Role: [REDACTED]
	Date of signature: 19-Dec-2024 21:03:28 GMT+0000

Reason for signing: Approved	Name: [REDACTED]
	Role: [REDACTED]
	Date of signature: 20-Dec-2024 19:35:56 GMT+0000

Signature Page for VV-TMF-3607081 v1.0

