7.2.1. Inclusion Criteria

A participant must meet the following criteria to be eligible for inclusion in the study:

1. Male or female adolescent or adult (≥ 12 years of age at time of screening visit)
2. Skin of color, defined as Fitzpatrick skin type ≥ 4 at screening visit
3. Diagnosis of AD according to American Academy of Dermatology consensus criteria at time of screening visit
4. EASI ≥ 16 at screening and baseline visits
5. IGA score ≥ 3 at screening and baseline visits
6. $\geq 10\%$ BSA of AD involvement at the screening and baseline visits
7. PP NRS ≥ 4 at baseline visit (weekly average over prior 7 days)

NOTE:

- Baseline PP NRS for maximum itch intensity will be determined based on the average of daily NRS scores for maximum itch intensity (the daily score ranges from 0 to 10) during the 7 days immediately preceding baseline. A minimum of 4 daily scores out of the 7 days is required to calculate the baseline average score. For participants who do not have at least 4 daily scores reported during the 7 days immediately preceding baseline, the baseline visit may be postponed until this requirement is met, but without exceeding the 35-day maximum duration for screening

8. Recent history (within 6 months before screening visit) of inadequate response of atopic dermatitis to topical prescription therapies or those therapies were inadvisable (eg, intolerance, because of important side effects or safety risks)

NOTE:

- Participants who are unable to achieve and/or maintain remission and low disease activity (comparable to IGA 0 = clear to 2 = mild) despite treatment with a daily regimen of medium to higher potency TCS (\pm TCI as appropriate), applied for at least 28 days of use, or for the maximum duration recommended by the product prescribing information, whichever is shorter, will meet the definition of inadequate response for the purpose of this study.
- Participants with documented systemic treatment for AD in the past 6 months are also considered as inadequate responders to topical treatments and are potentially eligible for treatment with dupilumab after appropriate washout.

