10. Assessments/procedures should be conducted in the following order: Patient-Reported Outcomes (PROs), investigator assessments, safety and laboratory assessments, administration of study drug. Clinical sites will check participant data collected on the diary. Topical emollient (moisturizer) should be applied twice daily, as per physician's recommendation starting at the screening visit. Participants should continue to apply moisturizers throughout the study. However, to allow adequate assessment of skin dryness, moisturizers should not be applied on the day of the study visit.

11. These assessments are to be completed by study participants in their diaries: Peak Pruritus NRS will be conducted daily starting 7 days prior to baseline. Sleep Quality NRS is to be collected daily for 7 days immediately preceding the baseline visit and all subsequent visits.
12. CDLQI for participants <16 years of age, DLQI for participants ≥ 16 years of age.
13. AD phenotypic description (primary morphologies, and distribution) includes the following: Localized AD, Flexural AD, Extensor AD, Nummular AD, AD with prurigo nodules, Follicular AD, Papular AD, Lichenoid AD, and Psoriasiform AD
14. A photography substudy will be performed at a subset of study sites. Site training will be provided. Participant/parents or legal guardians who agree to participate in the substudy will be required to sign a separate substudy informed consent/assent form for use of photographs for educational/marketing purposes before the procedure is performed.
15. A colorimetry substudy will be performed at a subset of study sites. Site training will be provided. Participant/Parents or legal guardians who agree to participate in the substudy will be required to sign a separate substudy informed consent/assent form before the measurements are performed.
16. An OCT substudy with additional non-invasive in vivo imaging including line field confocal OCT and/or reflectance confocal microscopy at the discretion of the investigator will be performed at a single study site. Participant/Parents or legal guardians who agree to participate in the substudy will be required to sign a separate substudy informed consent/assent form before the procedure is performed.
17. Any participant who experiences an AESI related to an eye disorder will be referred to an ophthalmologist if deemed necessary by the investigator.

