11. STATISTICAL PLAN

11.1. Statistical Hypothesis

There is no formal statistical hypothesis testing and no planned inferential comparisons in this study.

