6.3. Analysis Visit Window

Data analyzed by-visit-analysis (including all efficacy data, physical exam, vital signs, biomarker) will be summarized by the study scheduled visits described in the study protocol and SAP, "Schedule of Event". The analysis visit windows will be exhaustive so that all available values obtained from unscheduled visits, ET visits and EOT/EOS have the potential to be summarized.

The following analysis visit windows for all by-visit analysis will be used to map the unscheduled visits, ET and EOT/EOS visits, based on the study day:

visit	Targeted Study Days*	Analysis Window in Study Days
Screening	<1	<1
Baseline	1	1
Week 2	15	[2, 22]
Week 4	29	[23, 43]
Week 8	57	[44, 71]
Week 12	85	[72, 99]
Week 16	113	[100, 127]
Week 20	141	[128, 155]
Week 24(End of Treatment) (End of Study)	169	>=156

*study day is calculated relative to the date of first study drug injection.

In general, the following order will be used to select the record for analysis at a given visit:

3. Scheduled visit
4. Early termination (ET) or EOS, whichever comes first if scheduled visit is not available
5. Unscheduled visit if both scheduled visit and ET/EOT/EOS are not available

For the multiple measurements of the same test in the same window, the following rules will be used to pick up the analysis value:

- If multiple valid values of a variable are within an analysis visit window, the closest from the target study day will be selected.
- If the difference is a tie, the value after the targeted study day will be used.
- If multiple available values of a variable exist within a same day, then the first value of the day will be selected.

For the daily collected ePRO data, the analysis visit windows will be implemented following the procedure below:

Step 1: Derive the study day,

- If diary date \geq 1st injection date, then diary study day=diary date – 1st injection date +1;

- Otherwise diary study day=diary date – 1st injection date

Step 2: Windows are defined as -6 to 1 = BL, 2 to 8 = week 1, 9 to 15 = week 2, etc, with 7-day intervals between visit windows.

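### The SAP's Peak Pruritus baseline (day -6 to day 1, no minimum) does not match the protocol's (the 7 days before baseline, at least 4 scores), and the SAP gives Sleep Quality two different baseline windows

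*SAP*

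**What the plan says.** **Protocol, Peak Pruritus.** Inclusion criterion 7 (Protocol 7.2.1) requires a weekly average of at least 4. Its note takes that average from the daily scores "during the 7 days immediately preceding baseline" and adds: "A minimum of 4 daily scores out of the 7 days is required to calculate the baseline average score". If fewer than 4 are available, the baseline visit may be postponed within the 35-day screening limit. Footnote 11 to the Schedule of Events is in line with this: "Peak Pruritus NRS will be conducted daily starting 7 days prior to baseline".

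**SAP, Peak Pruritus.** SAP 10.3 defines the baseline as a prorated average over the days before and on the baseline visit ("i.e. study day -6 to day 1"). It states no minimum number of scores.

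**SAP, all daily diary data.** SAP 6.3, Step 2: "Windows are defined as -6 to 1 = BL, 2 to 8 = week 1, 9 to 15 = week 2", and so on in 7-day blocks.

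**SAP, Sleep Quality.** This is also a daily diary item, but SAP 10.3 sets its baseline as the week before the visit ("i.e. study day -7 to day -1"). It states no minimum either.

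**The concern.** There are two separate contradictions.

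- **Protocol against SAP.** The Peak Pruritus baseline used for analysis is not the one used to admit the participant. The window moves by one day, the minimum is absent, and the SAP neither acknowledges nor explains the change.
- **SAP against itself.** For Sleep Quality, SAP 6.3 and SAP 10.3 give different baseline windows. A programmer has to choose one.

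Four secondary Peak Pruritus endpoints depend on this baseline (Protocol 4.1.2): the 3-point and 4-point responses, the absolute change and the percent change. The 4-point response is the most exposed. A participant admitted at an average of 4 or just above, whose analysis baseline falls below 4, cannot improve by 4 points on a scale that stops at 0. SAP 5.7 still counts that participant in the denominator at every visit with a non-missing value. The Sleep Quality change endpoint is exposed only to the choice of window.

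**Working it through.** **Inputs from the documents**
- Day numbering (SAP 6.3, Step 1): the injection day is day 1 and the day before it is day -1, so there is no day 0.
- Windows: protocol day -7 to -1; SAP Peak Pruritus day -6 to 1.
- Daily score 0 to 10 (Protocol 9.2.2.1.1); minimum 4 of 7 and eligibility cut of 4 (Protocol 7.2.1).

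**1. Window length and overlap.** The SAP window is {-6, -5, -4, -3, -2, -1, 1}, which is 7 days, so the SAP's stated length is reproduced. The protocol window {-7, ..., -1} is also 7 days. They share days -6 to -1, or 6 of 7. Day -7 leaves and day 1 enters.

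**2. Complete diaries.** Let S be the sum over days -6 to -1.

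SAP baseline − protocol baseline = (S + day 1)/7 − (S + day -7)/7 = (day 1 − day -7)/7.

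The largest possible absolute difference is 10/7 = 1.43 points. A 1-point difference between the two days moves the baseline by 1/7 = 0.14.

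**3. Crossing the cut.** Take a participant with seven protocol scores summing to 28, so 28/7 = 4.0 and eligible. With day -7 = 5 and day 1 = 4, the SAP baseline is (28 − 5 + 4)/7 = 27/7 = 3.86. A 4-point reduction would need a weekly average of 3.86 − 4 = −0.14, which is off the scale.

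**4. Sparse diaries.** With exactly 4 protocol scores, one of them on day -7, 4 − 1 = 3 fall in days -6 to -1. If day 1 is also scored, the difference is (day 1 − day -7)/4, at most 10/4 = 2.5 points. Example: day -7 = 10, the other three sum to 6, day 1 = 0. Protocol: (10 + 6)/4 = 4.0. SAP: (6 + 0)/4 = 1.5. Three is also the floor: an eligible participant cannot have fewer than 3 scores in the SAP window.

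**5. How often it matters (illustrative).** The documents give no variability for daily scores, so these inputs are assumed: person means normally distributed, independent day-to-day noise, scores rounded and held to 0-10, entries missing at random, no trend across the eight days, 400,000 simulated people per setting. Results are for those eligible under the protocol rule.

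| Mean; between-person SD; day-to-day SD | Entries missing | SAP baseline below 4 | Mean absolute difference | Fewer than 4 scores in SAP window |
|---|---|---|---|---|
| 7; 1.8; 1.0 | 0% | 0.44% | 0.15 | 0% |
| 7; 1.8; 1.0 | 25% | 0.49% | 0.17 | 2.6% |
| 7; 1.8; 1.5 | 0% | 0.70% | 0.22 | 0% |
| 7; 1.8; 1.5 | 25% | 0.78% | 0.24 | 2.6% |
| 6.5; 2; 2 | 0% | 1.6% | 0.29 | 0% |
| 6.5; 2; 2 | 25% | 1.8% | 0.32 | 2.6% |

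On 120 participants, 0.0044 × 120 = 0.5 and 0.018 × 120 = 2.2: about half a participant to two.

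**The case against.** **The day 1 entry is defensible.** Peak Pruritus has a 24-hour recall, so entries on days -6 to 1 describe roughly the seven 24-hour periods that end at baseline. Protocol 9.2 puts patient-reported outcomes before dosing, and Protocol 9.2.2.1.1 collects the score on the baseline day as well as in the preceding week. The SAP blocks are also tidy: contiguous weeks, each ending on a target day. This stands as a reason the sponsor might prefer day -6 to 1. It does not reconcile that window with the protocol, or SAP 6.3 with the Sleep Quality rule.

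**A reader might infer that the baseline is contaminated by treatment.** SAP 6.1 compares only dates for data other than adverse events, so a diary entry made later on day 1 would count as baseline. But such an entry would still look back largely over hours before the injection, and the visit order puts questionnaires first. The documents support an ambiguity here and no material bias.

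**A reader might infer that a baseline could rest on one entry.** Not for an eligible participant: the protocol's 4-score rule leaves at least 3 scores in the SAP window. The SAP's wording about scores reported continuously for 7 days could even be read as requiring all seven, though proration points the other way.

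**A reader might infer that Peak Pruritus is out of line with the rest of the SAP.** Its window agrees with SAP 6.3; Sleep Quality is the exception. The conflict between the two items concerns the window only, since neither has a minimum.

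**A reader might want the 4-of-7 rule after baseline too.** Neither document sets one, and SAP 10.3 openly averages available scores, with a 3-score example, so nothing is contradicted. It would also be a trade-off: with non-missing values as the denominator (SAP 5.7), setting sparse weeks to missing removes those participants from the responder rates.

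**Stakes are low.** Protocol 11.1 says: "There is no formal statistical hypothesis testing and no planned inferential comparisons in this study". That stands.

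**Conclusion.** The point holds as two textual contradictions with a small numerical effect. The SAP's Peak Pruritus baseline differs from the protocol's in both window and minimum, and the SAP contradicts itself on the Sleep Quality window.

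The bounds of 1.43 points (complete diaries) and 2.5 points (exactly 4 eligible scores) follow from the definitions and the 0-10 scale alone; they are extremes. Typical differences of 0.15 to 0.32 points, and the 0.4% to 1.8% of eligible participants falling below 4, rest on the assumed means, SDs and missingness above. Fewer response classifications would change than that share suggests, because someone with a baseline of exactly 4.0 must reach a weekly average of 0 to be a 4-point responder.

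Only secondary diary endpoints are touched. The primary endpoint, EASI-75 at week 24, does not use the diary. No test, error rate or sample size is involved.

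**What to change.** In SAP 6.3 and 10.3, state one baseline window and one minimum for both daily diary items, Peak Pruritus and Sleep Quality.

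- **Default: follow the protocol.** Use day -7 to -1 with at least 4 of 7 scores, and treat the baseline as missing otherwise. Say that the day 1 entry belongs neither to baseline nor to week 1, so that the later blocks (days 2 to 8, 9 to 15 and onward) are unchanged.
- **If the sponsor keeps day -6 to 1,** declare it as a deviation from the protocol definition with its reason, apply it to Sleep Quality as well, and still state the minimum. Some eligible participants could then fall short of 4 scores: about 2.6% under the assumed 25% of missing entries.

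A post-baseline 4-of-7 rule could be offered as an optional sensitivity analysis for the pruritus responses; it is not needed to resolve the conflict.

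The cost is SAP wording and a small programming change, with no new data. Under the default, the Peak Pruritus minimum should remove no eligible participant. For Sleep Quality the minimum is an extension that the protocol does not set, so a few sparse baselines there could become missing.
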